## **Conclusions That May Be Drawn From The Study**

A conclusion may be made that there is an interventional superiority of the invisa-RED® IR REHAB over a Sham (placebo) device when employed as a therapy for the adjunctive treatment of nociceptive musculoskeletal pain, and that the invisa-RED® IR REHAB when used as directed is both clinically safe and effective.

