# **invisa-RED IR REHAB Clinical Trial Protocol**

## **Purpose of the Study**

The trial is designed to provide data with which to evaluate the efficacy and safety of the invisa-RED® IR REHAB Low-level Laser Therapy (LLLT) device as compared with a sham device when used for the adjunctive treatment of nociceptive musculoskeletal pain . This will be a single blind trial of two groups of equal number; one group will be treated as usual, the other treated using a sham device. At the conclusion of the trial; results from the two groups will be statistically analyzed to determine the efficacy of the IR REHAB machine for the adjunctive treatment of musculoskeletal pain.

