## **Methods and Procedures**

The trial is designed to prove the efficacy and safety of the invisa-RED Technology IR REHAB device when used as prescribed as an adjunctive therapy for musculoskeletal pain. The trial will compare results between two groups; the first will be treated using the invisa-RED Technology IR REHAB and the second group with a sham (placebo) device.

The trial will be conducted employing a single blind study methodology; participants will not know to which trial group they have been randomly assigned. Participants randomly selected for the control or Sham (placebo) Group will undergo therapy sessions with a disabled IR REHAB device producing no laser energy, however, this sham device will power up the console and fans to appear to be operating normally. If a participant questions the efficacy of the sham device, an assertion may be made that only a near infrared, non-visible frequency of light, is being employed. The control group receiving treatments using the sham device will be scheduled for treatment at times other than participants who will undergo therapy sessions with the fully functioning device in order to ensure the trial blind.

All participants will undergo treatments 2 times weekly for 3 weeks. Treatment will be 15 minutes each session. For each 15 minute session a singular adjustment to the laser’s power output will be made based on the participants standard Fitzpatrick Skin Type. This power adjustment ensures optimal photonic energy absorption, enhanced efficacy, and participant safety. The minimum time between any participants’ scheduled treatments will be 48 hours.

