## **Methods and Procedures - continued**

Prior to each therapy session the participant will be asked to record their pain level using a Visual Analog Scale (VAS) and then in the same manner after each treatment using the same Visual Analog Scale (VAS). The results from the two groups will be statistically analyzed to determine the efficacy of the invisa-RED Technology IR REHAB as an adjunctive therapy for nociceptive musculoskeletal pain. Any medical errors will be included in the statistical analysis.

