## **Monitoring Plan**

The study is classified as a minimal risk trial of short duration therefore a detailed plan for monitoring the data for participant safety is not required.

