## Adverse Effects Overview:

[figure not shown]
Edit	Time Frame	4 months	
	Adverse Event Reporting Description		
	Source Vocabulary Name for Table Default	[Not specified]	
	Collection Approach for Table Default	Non-systematic Assessment	
Edit	Arm/Group Title	IR REHAB Device	Sham Device
	Arm/Group Description	Participants will receive 6 treatments of 15 minutes each with an active IR REHAB device over the period of three weeks. IR REHAB: Participants undergo therapy sessions with active, dual wavelength, low level laser therapy device	Participants will receive 6 treatments of 15 minutes each with a disabled (sham) IR REHAB device over the period of three weeks. Sham: Participants undergo therapy sessions with disabled device producing no laser energy
	All-Cause Mortality	IR REHAB Device Affected / at Risk (%) 0/18 (0%)	Sham Device Affected / at Risk (%) 0/13 (0%)
Edit	Total		
	▼ Serious Adverse Events	IR REHAB Device Affected / at Risk (%) 0/18 (0%)	Sham Device Affected / at Risk (%) 0/13 (0%)
Edit	Total		
	Add Serious Adverse Event		
	▼ Other (Not Including Serious) Adverse Events	Frequency Threshold for Reporting Other Adverse Events 0%	
Edit		IR REHAB Device Affected / at Risk (%) 0/18 (0%)	Sham Device Affected / at Risk (%) 0/13 (0%)
Edit	Total		

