## Graphs Depicting Results - continued:

**Comparative Clinical Trial Results by Participant**

## Graphs Depicting Results - continued:

## Study Results

The “Clinical Trial to Establish the Safety and Efficacy of the IR REHAB Device When Used as an Adjunctive Therapy for Nociceptive Musculoskeletal Pain”

FDA Study NCT06393088, was designed to provide data with which to evaluate the efficacy and safety of the invisa-RED® IR REHAB Low-level Laser Therapy (LLLT) device as compared with a sham device when used for the adjunctive treatment of musculoskeletal pain. This single blind trial of two groups; one group treated as usual, the other treated using a sham device. At the conclusion of the trial; results from the two groups were statistically analyzed to determine the efficacy and safety of the invisa-RED® IR REHAB machine for the adjunctive treatment of nociceptive musculoskeletal pain.

The study was designed as a superiority trial with a null hypotheses which asserted, in the population where the sample was obtained there was no difference between the intervention (IR REHAB) and placebo (Sham Device) groups in the mean change in the primary outcome variable:

However, the results of a bootstrapped (N=20,000) independent samples 2 sided t-test revealed:

An estimated mean difference (net value) of 41.67% greater reduction in participant's pain level when using the invisa-RED® IR REHAB as compared to the Sham Device this with a 95% confidence level from 20.15% to 61.67% and a two tailed P value < 0.01.

Therefore by conventional criteria the results are considered to be statistically significant for the trial's primary outcome variable, disproving the null hypotheses and affirming the alternative hypotheses that there exists an interventional superiority of the invisa-RED® IR REHAB therapy over the Sham Device (placebo).

Additionally and of great significance, there were zero adverse effects or mortality reported during or after the the clinical trial.

Three additional bootstrapped analysis (N=20,000) of the data were conducted:

- 1) An independent samples effect size analysis was conducted using Cohen's d and resulted in a value of 1.44, which by convention indicates a large effect size for the invisa-RED® IR REHAB over a placebo.

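### The conclusion calls the device clinically safe without stating sample size, ascertainment or uncertainty, and the statistical safety analysis that the results describe is not shown

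*Combined protocol and SAP*

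**What the plan says.** Safety is a stated aim. Methods and Procedures opens with "The trial is designed to prove the efficacy and safety of the invisa-RED Technology IR REHAB device", and Purpose of the Study also names safety. The planned statistical analysis is narrower: in Purpose of the Study, "results from the two groups will be statistically analyzed to determine the efficacy of the IR REHAB machine", with no mention of safety.

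Two other provisions bear on safety:

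- Methods and Procedures - continued says "Any medical errors will be included in the statistical analysis", without a variable, definition or method.
- Monitoring Plan says that "a detailed plan for monitoring the data for participant safety is not required", because the trial is classed as minimal risk and short.

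Adverse Effects Overview gives deaths, serious adverse events and other adverse events as 0/18 in the active arm and 0/13 in the sham arm. The collection approach is "Non-systematic Assessment" and the time frame is 4 months.

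Study Results then says "results from the two groups were statistically analyzed to determine the efficacy and safety of the" device, and adds: "Additionally and of great significance, there were zero adverse effects or mortality reported during or after" the trial. Conclusions That May Be Drawn From The Study ends by saying that the device "when used as directed is both clinically safe and effective".

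**The concern.** The last section states a safety conclusion as firmly as the efficacy conclusion, but the support for the two is very different. Efficacy has a hypothesis, a test, a confidence interval and a power statement. Safety has a row of zeros, a label saying that collection was not systematic, and no interval.

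Zero reports in a group this small are compatible with harms that are not rare. A reader who sees only the results narrative and the conclusion learns neither how many people were exposed, nor how events were sought, nor how high the true rate could be. That reader is also told that safety was statistically analysed, and no such analysis appears. What is at stake is the wording of a headline conclusion on a declared aim. The pain comparison is not affected.

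**Working it through.** **Step 1. What was planned and reported for safety.**

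| Section | Subject |
|---|---|
| Study Research Questions; Null and Alternative Hypotheses | Pain |
| Data Analysis and Data Monitoring | t-test on change in pain |
| Analysis | t-test on change in pain (100 mm VAS) |
| Outcome Measures - continued | Power, p-value and interval for pain |
| Study Results, additional analyses | Cohen's d, Mann-Whitney and Levene, all accompanying the pain comparison |
| Methods and Procedures - continued | Medical errors: no method given, no result reported |
| Adverse Effects Overview | Zero counts per arm, no interval, no comparison |

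The only safety result is the last row.

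**Step 2. The document's own figure.** 0/18 = 0% and 0/13 = 0%, as printed. The reporting threshold for other adverse events is 0%, so the zeros are not produced by a cut-off. No confidence limit for safety is stated anywhere, so there is none to reproduce.

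**Step 3. Denominators.**

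| Section | Active | Sham | Total |
|---|---|---|---|
| Adverse Effects Overview (at risk) | 18 | 13 | 31 |
| Participant Flow (started) | 16 | 15 | 31 |
| Participant Flow (completed); Reporting Groups | 16 | 13 | 29 |

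The adverse-event table and the participants who started both total 31, but the split by arm differs. The document does not show which split is right, so both are carried forward. Only 0/18 is printed for the active arm. The 0/16 below combines the printed zero with the arm size in Reporting Groups and Participant Flow.

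**Step 4. Upper limit for the true event rate.** With zero events in n participants, the exact (Clopper-Pearson) upper limit is 1 − 0.025^(1/n) for a two-sided 95% interval and 1 − 0.05^(1/n) for a one-sided 95% limit.

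| Arm and n | Two-sided 95% | One-sided 95% |
|---|---|---|
| Active, 18 | 1 − 0.025^(1/18) = 18.5% | 1 − 0.05^(1/18) = 15.3% |
| Active, 16 | 1 − 0.025^(1/16) = 20.6% | 1 − 0.05^(1/16) = 17.1% |
| Sham, 15 | 21.8% | 18.1% |
| Sham, 13 | 24.7% | 20.6% |

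For the active arm, the rule of three (3/n) gives 16.7% and 18.8% for n = 18 and 16, and the Wilson upper limit gives 17.6% and 19.4%. Every variant leaves rates of about 15% or more unexcluded.

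**Step 5. How easily zero arises.** The chance of no event in n participants is (1 − p)^n.

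- n = 16: 0.95^16 = 44% if the true rate is 5%; 0.90^16 = 19% if it is 10%.
- n = 18: 0.95^18 = 40% and 0.90^18 = 15%.

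**The case against.** The strongest reply is that the document is more careful than the criticism suggests.

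- The conclusion is conditional on use as directed, and Study Results speaks of events reported. This is true, so it would be wrong to call the statement wholly unqualified. But a condition of use says nothing about how many people were observed or how uncertain the result is.
- Adverse Effects Overview openly gives the counts, denominators and collection method. This also stands. The weakness is that neither the narrative nor the conclusion carries them over.
- Item VIII of Risk/Benefit Assessment - cont. has each patient attest to comfort at the start of every session and report any skin discomfort. A reader might therefore object that local harms were actively sought. The text describes a treatment safeguard and does not say that the answers were recorded or analysed. The document's own label for collection remains non-systematic.
- The minimal-risk classification may explain why there is no detailed monitoring plan. It is an assessment made before the trial and does not add to what the trial observed.
- The figure of about one in five depends on the choice of limit and covers events of any severity. That is fair. The one-sided limits are lower, at 15.3% and 17.1%, and the conclusion is the same.

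A reader might go further and infer that the device is unsafe, that events occurred and were missed, or that nobody was followed after the three weeks of sessions. The documents support none of these. No event is reported, non-systematic collection leaves capture unassured without showing that it failed, and some pages are not available for review. The basis of the 4-month time frame is a question for the sponsor.

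**Conclusion.** The point holds, as one about what is claimed. The trial shows no reported events in 16 or 18 active participants. That is compatible with a true event rate of up to 18.5% (n = 18) or 20.6% (n = 16) on the exact two-sided limit. These figures assume that every event was captured and that participants are independent with a common event rate. If capture was incomplete, the true rate could be higher still. The statement that safety was statistically analysed has no counterpart in the plan or the results beyond descriptive counts.

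This should be corrected because safety is a declared aim and the sentence stands in the conclusions. It does not invalidate the trial: no pain estimate, test or analysis population changes.

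**What to change.** 1. Check the arm sizes in Reporting Groups, Participant Flow and Adverse Effects Overview against source records, and use one safety N per arm.
2. In Conclusions That May Be Drawn From The Study, remove the words calling the device clinically safe and add a separate sentence: *No adverse events were reported among N active participants (exact two-sided 95% upper limit X%), collected by non-systematic assessment; event rates below this limit cannot be excluded.* X is 18.5% if N = 18 and 20.6% if N = 16.
3. Put the same limit beside the zero-adverse-effects sentence in Study Results.
4. In the Study Results sentence on what was statistically analysed, delete the reference to safety, or report per-arm counts with exact limits, labelled post hoc.

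As a query only, ask the sponsor how the 4-month time frame was covered.

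The cost is a check of source records, a few lines of text and one limit per arm. No new data, visits or participants are needed. The downside is a more modest safety claim.

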## **Data Analysis and Data Monitoring**

The mean change in each group of participant's pain levels as recorded at the trials beginning and then at the trials conclusion will be statistically evaluated using a two-tailed independent sample T-test with an a priori threshold p value of < (less than) 0.05.

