### **Risk/Benefit Assessment - cont.**

- IV) The device is NOT for a use of substantial importance in diagnosing, curing, mitigating, or treating disease, or otherwise preventing impairment of human health that presents a potential for serious risk to the health, safety, or welfare of a subject.
- V) The invisa-RED Technology IR REHAB is to be used only as directed as an adjunctive therapy for nociceptive musculoskeletal pain.
- VI) The device does NOT otherwise present a potential for serious risk to the health, safety, or welfare of a subject.
- VII) The invisa-RED IR REHAB is classified as an FDA Class II device and has passed all FDA electromagnetic compatibility (EMC) standards.
- VIII) The invisa-RED IR REHAB device employs Class 3b laser diodes in a system of "paddles" each containing multiple diodes. Class 3B lasers are hazardous for eye exposure; therefore during therapy protective eyewear is prescribed for staff, the individual undergoing treatment, and any others in the room. Eye safety is further enhanced by standardized invisa-RED Technology IR REHAB clinical procedures, which are designed to eliminate exposure of the eyes of the patient and any proximate individuals to direct laser light. IR REHAB clinical procedures which are found in the manual and are stressed as mandatory during user training dictate that the paddles are to be 1) placed on the area to be treated, 2) secured if required, and then and only then 3) the system is activated and treatment begun. This greatly reduces the chance of any direct laser light entering the eye. Class 3B lasers can heat skin and materials but are not considered a burn hazard. Treatment protocol standards do dictate power settings be adjusted for the patient's Fitzpatrick Scale skin type; as differing skin tones result in a variance in their coefficient of absorption of photonic energy. If these recommendations are not followed the therapy may result in skin sensitivity. Additionally each patient is asked to verbally attest to his or her comfort level at the start of each therapy session and further instructed to notify staff of any skin discomfort at any time during the treatment.

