## **Analysis**

To examine the research question, independent sample *t*-tests using the statistical analysis program IBM SPSS ver.30 will be conducted on the data set. The data set will be comprised of comparative results from the two trial groups, the Care as Usual Study Group and the Sham (placebo effect) Study Group. The tests will be bootstrapped to a test size of N=20,000 for validation.

An independent samples *t*-test is the appropriate statistical test when the purpose of research is to assess if differences exist on a continuous (interval/ratio) dependent variable by a dichotomous (2 groups) independent variable. The continuous dependent variable to be tested is the change in pain level of the joint or body area treated during the clinical trial. Each participant will be asked to indicate on a standard 100mm Visual Analog Scale their pain levels before the first treatment and after each of the prescribed treatments. The difference between the initial pain level of a participant and the level of pain indicated after their sixth and final treatment will be statistically analyzed to determine if there is a significant difference between those in the Care As Usual Group and the Sham (placebo) Group.

The dichotomous independent variables for the data set is the change in pain level of each participant in the group treated with the invisa-RED Technology IR REHAB Low-level Laser Therapy (LLLT) device and the group treated using the sham (placebo) device as a therapy in the standardized clinical protocol. The assumptions of normality and homogeneity of variance will be assessed. Homogeneity of variance assumes that both groups have equal error variances and will be assessed using Levene's Test for the Equality of Error Variances. Each *t*-test will be two tailed with the probability of rejecting the null hypothesis when it is true set at  $p < 0.05$ . This ensures a 95% certainty that the differences did not occur by chance. Data produced by both groups will be the results of a clinical trial governed and conducted as a randomized single - blind study using an IRB approved clinical protocol.

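### The conclusion that the device is clinically safe is not supported: zero events in 16 (or 18) active participants leaves rates up to about one in five open, and the at-risk counts conflict with participant flow

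*Combined protocol and SAP*

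**What the plan says.** Safety is a stated aim. Purpose of the Study says the trial is "designed to provide data with which to evaluate the efficacy and safety" of the device, and Methods and Procedures goes further: "The trial is designed to prove the efficacy and safety".

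The analysis plan covers pain only. In Data Analysis and Data Monitoring, mean pain change is to be "statistically evaluated using a two-tailed independent sample T-test". The Analysis section says "The continuous dependent variable to be tested is the change in pain level". The one other item named for analysis is in Methods and Procedures - continued: "Any medical errors will be included in the statistical analysis". Medical errors are not adverse events.

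On safety data, the Monitoring Plan says that, for a short, minimal-risk trial, "a detailed plan for monitoring the data for participant safety is not required". Risk/Benefit Assessment - cont. says "each patient is asked to verbally attest to his or her comfort level at the start of each therapy session", and that patients are also told to report skin discomfort to staff at any point during treatment.

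In the results, the Adverse Effects Overview gives 0/18 active and 0/13 sham for deaths, serious events and other events, over a 4-month time frame, with collection labelled non-systematic. Study Results stresses the absence of reported events. The Conclusions section then says the device "when used as directed is both clinically safe and effective".

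**The concern.** A zero count is an observation. A claim of safety needs either an acceptable event rate to compare it with or, at the least, a limit on what the data exclude. The documents give neither, although Study Results says the data were statistically analysed for safety as well as efficacy. With about 16 people exposed, no reported events is compatible with a fairly common adverse effect.

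The table a reader would use to judge this also disagrees with Participant Flow. If the adverse event table has the arms right, the two participants who withdrew were on the active device, where Participant Flow reports no withdrawals. For a safety conclusion, the arm and the reason for leaving both matter.

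**Working it through.** **Step 1: check the printed at-risk counts.**

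| Source | Active | Sham | Total |
|---|---|---|---|
| Participant Flow, started | 16 | 15 | 31 |
| Participant Flow, completed | 16 | 13 | 29 |
| Reporting Groups; Baseline Characteristics; Outcome Measures | 16 | 13 | 29 |
| Adverse Effects Overview, at risk | 18 | 13 | 31 |

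The active count of 18, printed in all three rows of the adverse event table, matches no other count. The sham count of 13 matches completers but not starters. However, 18 + 13 = 31 = 16 + 15. This is what would result if the two withdrawals were assigned to different arms in the two tables.

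The other sections do not decide the matter. Those that give 16 and 13 total 29, so they count completers, and 16 active completers fit either 16 or 18 active starters. Only Participant Flow puts the active starters at 16.

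**Step 2: limits for zero events.** The exact upper limit for 0 events in n is 1 − 0.025^(1/n) for a two-sided 95% interval and 1 − 0.05^(1/n) for a one-sided 95% bound. The confidence level is the reviewer's choice, since the documents give no interval for adverse events.

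| Arm and n | Two-sided 95% upper limit | One-sided 95% upper limit |
|---|---|---|
| Active, 16 | 1 − 0.025^(1/16) = 20.6% | 1 − 0.05^(1/16) = 17.1% |
| Active, 18 | 1 − 0.025^(1/18) = 18.5% | 1 − 0.05^(1/18) = 15.3% |
| Sham, 15 | 1 − 0.025^(1/15) = 21.8% | 1 − 0.05^(1/15) = 18.1% |
| Sham, 13 | 1 − 0.025^(1/13) = 24.7% | 1 − 0.05^(1/13) = 20.6% |

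**Step 3: how informative is a zero?** If the true rate were 10%, the chance of no event would be 0.90^16 = 18.5% with 16 exposed and 0.90^18 = 15.0% with 18. At a true rate of 5% it would be 0.95^16 = 44.0% or 0.95^18 = 39.7%. To bring the two-sided limit down to 5% would take ln(0.025)/ln(0.95) = 71.9, so about 72 event-free participants.

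**Step 4: comparison with sham.** For 0/16 against 0/15, the Newcombe 95% interval for active minus sham runs from −20.4 to +19.4 percentage points, so the sham arm adds little.

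**Step 5: how events were sought.** Treatment lasted three weeks and the adverse event time frame is 4 months. The documents do not say that answers to the comfort check were recorded, or how participants were asked about events after the sixth session. The limits in step 2 assume complete capture. Any missed events would make them too low, by an amount the documents do not allow one to estimate.

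**The case against.** The best defence is that the trial was judged minimal risk with reasons given, that lighter monitoring follows from that, and that participants were seen six times, asked about comfort at the start of each session and told to report skin discomfort during treatment. That is repeated contact about the main skin risk the protocol names, and it deserves credit. No planning error is shown in the Monitoring Plan. But minimal risk is a judgement made before the trial, not evidence from it, and the report itself labels event collection non-systematic.

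It can also be said that the limit covers any event, however mild, and that the less strict one-sided figure is 17.1%. Both are true. With no acceptable rate defined, 20.6% does not by itself separate safe from unsafe. That is also why the claim of safety cannot stand.

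On the counts, a reader might infer that 18 is simply a slip for 16, or that the sham 13 is plainly wrong. The documents support neither. The matching total of 31 makes a misplaced pair of withdrawals a real possibility. Nor does any section say whether the two who withdrew received a session, so 13 could be a legitimate count of those treated with sham. A 16/15 split fits the planned equal groups better than 18/13, but that is not proof.

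**Conclusion.** The safety conclusion goes beyond the data. No adverse events were reported, and that statement stands. What the data exclude, assuming complete capture and independent participants, is an active-arm rate above 20.6% if 16 were exposed or above 18.5% if 18 were. The finding is the same on either denominator.

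The at-risk counts conflict with Participant Flow, and which table is right cannot be determined from the documents.

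A reader might go further and infer that the device is harmful, that events were concealed, or that non-systematic collection puts the true limit at some specific higher figure. Nothing in the documents supports the first two, and no capture rate is given from which to calculate the third. This is a finding about interpretation and reporting that should be corrected, not a fault in the design.

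**What to change.** 1. Reconcile the Adverse Effects Overview with Participant Flow against the source records. Establish the arm of the two who withdrew, whether they were treated, and when and why they left. Then report events among all who started, or all who were treated, and state which.
2. Give exact 95% limits by arm on the reconciled denominators, labelled post hoc because no safety analysis was planned.
3. In the Conclusions section, replace the safety claim with wording such as: *no adverse events were reported in [n] participants treated with the active device, under non-systematic collection; even with complete reporting, rates up to about [limit] are not excluded.* The limit is 20.6% if n = 16 and 18.5% if n = 18, and should be filled in only after step 1.
4. Optionally, tone down the emphasis on the zero count in Study Results. Once the limits are shown, this is a matter of style.

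The cost is a check of the paper records of 31 participants, one limit per arm and one rewritten sentence. No new data are needed. The downside is that the report can no longer say safety was shown.
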